13.5 Clinical Safety Laboratory Investigations

Not Applicable.

13.6 Concomitant Medication

The numbers and percentages of subjects reporting concomitant medications will be tabulated overall and by vaccine group and study period (treatment / Follow-up). Medications (generic drug name) will be coded using the World Health Organization (WHO) Drug dictionary (see [section 8.7](#) for definition).

14. INTERIM ANALYSIS

14.1 Interim Analysis

As the circulation of influenza viruses is seasonal and the rates of influenza are difficult to predict, this study is group sequentially designed with maximally 2 interim analyses planned over the course of the study. The goal of Interim Analyses is, first, to minimize the risk of not being able to take a significant test decision after the end of the study, and second, to be able to stop the study for early evidence of efficacy or for futility after observing at least 50% of planned RT-PCR confirmed influenza cases.

The data that will be included for the interim analysis will be derived from the EDC forms (Demographics, Vaccination, ILI Report) and external lab data from [REDACTED] (ILI Swab form). For the purpose of the interim analysis, the data are not required to be completely clean, frozen and locked but as clean as possible:

- 1) A snapshot would be acceptable for the purpose of this interim analysis.
- 2) EDC data part of the Interim Analysis should be 100% SV complete.
- 3) There should be no open / unanswered queries and should be considered clean following the ongoing data review process.
- 4) Lab data reconciliation EDC <> Laboratory Operations Management System (Lomas) should have no discrepancies.
- 5) Lab data [REDACTED] <> Lomas should have no discrepancies.

Any exceptions to the above requirements are to be reviewed by the study team and confirmed acceptable prior to taking the interim data snapshot. Freezing and Locking of the forms in Inform is not required. PI signatures are also not required. The first interim analysis will be performed after observing approximately 50% of planned RT-PCR confirmed influenza cases. In addition, DMC may request an additional interim analysis if deemed necessary.

- If the number of first-occurrence RT-PCR confirmed influenza cases from 21 through 180 days after vaccination or until the end of the influenza season, whichever is longer, is less than or equal to 119, no interim analysis for efficacy and futility will be done and the study will be continued because the probability to make a conclusion for futility or efficacy is too low.
- If the number of first-occurrence RT-PCR confirmed influenza cases from 21 through 180 days after vaccination or until the end of the influenza season, whichever is longer, is greater or equal to 120 but less than 238 unblinded interim analyses for efficacy and futility will be performed by the DMC (see below for description).

- If the number of first-occurrence RT-PCR confirmed influenza cases from 21 through 180 days after vaccination or until the end of the influenza season, whichever is longer, is greater or equal to 238 (targeted number of cases to be able to evaluate the primary objective) the trial will be stopped, data will be unblinded and the final analysis will be performed by the Sponsor. If the trial proceeds to the final analysis (upon reaching 238 cases) the boundaries for acceptance or rejection are identical to the assumed type 1 and type 2 errors for the overall design, and the trial stops to either reject or not reject the null hypothesis of the primary objective. That is, the primary objective, i.e. VE against RT-PCR confirmed influenza A and or B will be assess the one-sided 0.025 alpha level.

If the DMC states that the observed data provides already the full information level needed for the final test decision, then the final analysis can be done on full alpha level of one-sided 0.025 and no further enrollment is needed. However if the decision of the group-sequential test is to continue the study then it is on the DMC to determine the number of subjects needed to be additionally enrolled. The DMC should not be influenced by the results of the efficacy testing at the interim analysis when planning further subjects' accrual or the times of future analysis. Only the overall number of cases is allowed to be used for further planning. The following formula for determination of sample sizes for further enrollment may be used:

$$N_{\text{total}} = (C_{\text{planned}} - C_{\text{observed}}) / ER,$$

where N_{total} denotes the total number of subjects needed for further enrollment, C_{planned} is the overall number of cases needed for the test, i.e. 238 cases, C_{observed} is the number of cases observed at current stage, and ER is the observed total attack rate for both groups combined. A drop-out rate of 10% should be added.

For the analysis of early stopping for futility and for efficacy, an error-spending function will be applied to provide statistical stopping rules for efficacy (α -boundaries) and futility (β -boundaries) for the first interim analysis and second interim analysis, if necessary, based on the information accumulated until that specific interim stage, i.e. based on the accumulated variance of the parameter of interest.

These boundaries will be calculated on a p-value scale ([SAS/STAT 9.2 user's guide](#), the SEQDESIGN Procedure)

At each interim stage, α -boundaries, forming the adjusted probabilities for the type 1 error, are calculated using error-spending function and if the p-value for the test of primary objective is lower than the respective α -boundary the trial stops for efficacy at this stage. Using the same error-spending-function applied on the overall type 2 error of 0.1 (Power 90%), β -boundaries are calculated, i.e. the adjusted probabilities for

the type 2 error β , and if the p-value is higher than the β -boundaries, the trial stops early for futility at this stage.

In other words the trial stops early for efficacy if data collected at this stage allows to demonstrate primary efficacy objective (reject null-hypothesis); and the trial stops early for futility, if the data provides sufficient evidence that the test vaccine is not good as expected (the alternative hypotheses of absolute vaccine efficacy over the protocol-specified margin is not true, i.e $VE < 0.4$). Otherwise, the trial continues to the next stage and more subjects will be enrolled.

The cumulative O'Brien-Fleming type error-spending-function (Lan and DeMets, 1983; option ERRFUNCOBF in SAS[®] PROC SEQDESIGN) will be used for both α - and β -boundaries; the error-spending function is defined as:

$$E(t; a) = \begin{cases} 1 & \text{if } t \geq 1 \\ \frac{1}{a} 2 (1 - \Phi(\frac{z(1-a/2)}{\sqrt{t}})) & \text{if } 0 < t < 1 \\ 0 & \text{otherwise} \end{cases}$$

where a equals α for α spending function and β for beta spending function, and where t is the information fraction.

With a specified type 1 error, α , and information level t at stage k , the cumulative error is $\alpha E(t; \alpha)$ (as per page 69 of [SAS/STAT 9.2 User's guide](#), the SEQDESIGN Procedure)

If the trial proceeds to the final analysis, the boundary for rejection of null hypothesis is identical to the type 1 error (that is as the 0.025 one-sided alpha level)) with power specified for the overall design, and the trial stops to either reject or not reject the null hypothesis of the primary objective.

Additional interim analyses may be requested by the DMC, particularly if the first interim analysis is conducted soon after 119 cases of influenza have been reported. In this case, the DMC may request that a second interim analysis be conducted to allow for greater accuracy to determine if the trial should stop or continue.

Table 1 shows the needed total number of cases at each stage of the two-stage design together with boundaries for early stopping for futility or efficacy, calculated on p-value scale using the cumulative error spending function. With $\frac{1}{2}$ information collected at the stage of interim analysis (that is, with exactly 119 confirmed ILIs) the trial would stop early for futility at this stage in case a p-value higher than 0.35022 is observed, or it would stop early for efficacy if the p-value is lower than 0.00625. Otherwise the trial will be continued and more subjects will be enrolled. The actual boundaries used for decision

making would depend on number of confirmed ILIs occurring and reported for Interim Analysis.

Table 1: Example of a Two Stages Group-Sequential Design

	Stage 1 First Interim	Stage 2 Final
Number of Events	119	238
Alpha Boundary on p-value scale (equivalent to Type 1 error, 1-sided), early stopping for efficacy	0.00625	0.02275
Beta Boundary on p-value scale (equivalent to Type 2 error, 1-sided), early stopping for futility	0.35022	0.02275

The stopping rules are statistically determined and should be complemented by clinical and strategic stopping rules that allow the DMC to make a decision on a broader picture of the data which includes safety endpoints and the other endpoints of the study. Another interim look at the data with appropriate adjustment of type 1 error might be recommended before reaching the targeted 238 cases.

For the interim analyses, if needed a restricted unblinding will be done, i.e. only independent DMC members and unblinded individuals responsible for the analyses will receive access to the randomization codes and unblinded data for the purpose of preparing the interim analyses (further information on handling of the blinding for the interim analyses can be found in the DMC charter). The results of the interim analyses will be used only for DMC purposes and will not be reported in a CSR.

The comparison of the test statistic with its boundary values will be performed by using the SAS® SEQTEST procedure. The boundary information tables calculated by PROC SEQDESIGN at an analysis stage are structured for input to the SEQTEST procedure. At each subsequent stage, the boundary values are derived by using the test information tables created by the SEQTEST procedure at the previous stage. These test information tables are also structured for input to the SEQTEST procedure. PROC SEQTEST can also be used to compute parameter estimates, confidence limits, and p-values after the trial stops.

For the complete list of tables, figures and listings (TLFs) for interim analysis, please refer to the Table of Contents (TOC) for Interim Analysis stored in the eTMF.

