- If the number of influenza cases is greater or equal to 238 (targeted number of cases to be able to evaluate the primary objective) the trial will be stopped, data will be unblinded and the final analysis will be performed by the Sponsor. If the trial proceeds to the final analysis (upon reaching 238 cases) the boundaries for acceptance or rejection are identical to the assumed type 1 and type 2 errors for the overall design, and the trial stops to either reject or not reject the null hypothesis of the primary objective.

In case DMC states that the observed data provides already the full information level needed for the final test decision, then the final analysis can be done on full alpha level and no further enrolment is needed. However if the decision of the group-sequential test is to continue the study then it is on the DMC to determine the number of subjects needed to be additionally enroled. The monitoring committee should not be influenced by the results of the efficacy testing at the interim analysis when planning further subjects' accrual or the times of future analysis. Only the overall number of cases is allowed to be used for further planning. The following formula for determination of sample sizes for further enrolment may be used:

$$N_{\text{total}} = (C_{\text{planned}} - C_{\text{observed}}) * 200 / (ER_{\text{aQIV}} + ER_{\text{Comp}}),$$

where N_{total} denotes the total number of subjects needed for further enrolment, C_{planned} is the overall number of cases needed for the test, i.e. 238 cases, C_{observed} is the number of cases observed at current stage, and ER are the respective ER s assumed for each treatment group, i.e. 1.4 for aQIV and 3.5 for non-influenza comparator. A drop-out rate of 10% should be added.

For the analysis of early stopping for futility and for efficacy, an error-spending function will be applied to provide statistical stopping rules for efficacy (α -boundaries) and futility (β -boundaries) for the first interim analysis and second interim analysis, if necessary, based on the information accumulated until that specific interim stage, i.e. based on the accumulated variance of the parameter of interest.

These boundaries will be calculated on a p-value scale (
<https://support.sas.com/documentation/onlinedoc/stat/131/seqdesign.pdf>)

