5. SAMPLE SIZE AND POWER CONSIDERATIONS

Efficacy objectives:

Sample size and power consideration for the aQIV efficacy objective is based on criteria for demonstrating efficacy in placebo controlled studies provided in CBER guidance, specifically that the study should be powered to assess the lower bound of the two-sided 95% CI of vaccine effectiveness, anticipated to be substantially above zero. This study is planned using a group sequential design. The power of Cox Regression which is planned to be used for analysis is dependent on the overall number of influenza cases, so the sample sizes on number of subjects described in this section is provided more for operational reasons. Additional information on the planning of number of subjects that may need to be enrolled if it is decided to continue enrolment after interim analyses is described in [Section 8.6](#).

For the primary efficacy objective: with 1-sided alpha of 2.5% and assuming an attack rate of influenza of 3.5% among subjects enrolled in the non-influenza comparator group and 1.4% among the aQIV group, i.e. 60% assumed vaccine efficacy for aQIV, 238 events (i.e. 4,860 subjects per group under the assumed ERs) are needed with 86.5% power to show the absolute efficacy of aQIV versus non-influenza comparator, in preventing first occurrence RT-PCR-confirmed influenza A and/or B, due to any strain of influenza regardless of antigenic match to the strains in aQIV, in subjects ≥ 65 years of age, using a margin of 40% for lower bound of the CI for absolute vaccine efficacy.

For the first secondary efficacy objective: with a group vaccine efficacy of 65% but expecting conservatively reduced event rates of influenza cases due to matched strains of 2.5% among subjects in the non-influenza comparator group and 0.9% among the aQIV group then 144 events has estimated power approximately 88.5% to show the absolute efficacy of aQIV versus non-influenza comparator, using a margin of 40% for lower bound of the CI.

Assuming a drop-out rate of 10%, approximately 10,692 subjects ≥ 65 years, 5,346 per vaccine group will be randomized to receive either aQIV or non-influenza comparator (Boostrix®) in a 1:1 allocation ratio, stratifying by age (≥ 65 to 74 and ≥ 75 years of age), study site and by low vs high risk of influenza complications (score < 50 vs ≥ 50).

Immunogenicity objective:

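### An undefined full-information clause could let an interim look at 120 to 237 cases be tested at the full one-sided 0.025; type I error could reach about 4% if the clause were used selectively near 120 cases

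*SAP*

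**What the plan says.** Both documents set out three case-count rules (SAP 14.1, Protocol 8.6): no interim analysis at 119 cases or fewer; unblinded interim analyses by the DMC from 120 to 237 cases; stop and run the final analysis at 238 or more. At most two interim analyses are planned.

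A further sentence follows these rules. If the DMC states that the data already supply full information, the SAP continues: "then the final analysis can be done on full alpha level of one-sided 0.025 and no further enrollment is needed". The Protocol's version is "then the final analysis can be done on full alpha level and no further enrolment is needed". Neither document gives a threshold, says who calculates it, or says whether the declaration precedes unblinding. The next sentence turns to the case in which the group-sequential test says to continue.

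The surrounding plan is stricter:

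- The printed O'Brien-Fleming-type spending function releases the whole alpha only at an information fraction of 1 or more.
- For exactly 119 cases, described as half information, the SAP says that "it would stop early for efficacy if the p-value is lower than 0.00625".
- SAP 12.1 says that after an interim analysis that does not stop the trial, later analyses use a reduced alpha.

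**The concern.** At 238 or more cases the trial stops anyway, so a clause about having enough information already, with no more enrolment needed, has its natural use below 238. There it replaces a small spending boundary with 0.025. The declaration is made by the body that sees the unblinded efficacy data, and no criterion in these documents limits it.

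The primary claim is confirmatory: the lower confidence limit for VE must exceed 40%. If that claim could rest on an interim p-value between the spending boundary and 0.025, with a second chance at 238 cases otherwise, a reader could not verify the stated 2.5% one-sided error. The clause also conflicts with SAP 12.1 if it is used at a second look.

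**Working it through.** **Inputs.** From SAP 5: "with 1-sided alpha of 2.5% and assuming an attack rate of influenza of 3.5% among subjects"; "60% assumed vaccine efficacy for aQIV, 238 events (i.e. 4,860 subjects per group under the assumed ERs) are needed with 86.5% power"; "using a margin of 40% for lower bound of the CI for absolute vaccine efficacy"; randomisation "in a 1:1 allocation ratio". So the null HR is 0.6, the alternative HR is 0.4, and the target is 238 events. From SAP 14.1, Table 1: interim boundary 0.00625, futility 0.35022, final 0.02275. The final level appears as 0.02275 in the table and 0.025 in the text, so both are carried through.

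**Reproducing the plan's figures.** With Schoenfeld variance the drift at 238 events is √(238/4) × ln(0.6/0.4) = 3.128. A single look at 0.025 gives power Φ(3.128 − 1.960) = 87.9%. The two-stage design with the Table 1 boundaries at t = 0.5 gives 86.45%, matching the stated 86.5%. At zero drift the same boundaries give type I error 2.50% with binding futility and 2.59% if futility is ignored. The model therefore describes this design.

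**What the spending plan allows early.** The printed formula gives cumulative alpha 2[1 − Φ(2.2414/√t)], where 2.2414 is the normal point for 1 − 0.025/2. At 120 cases, t = 120/238 = 0.504, which gives 0.0016. At 178 cases (t = 0.748) it gives 0.0096, and at 220 cases (t = 0.924) 0.0197. Table 1 has 0.00625 at 119 cases. It does not follow from the printed formula, which is a separate matter.

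**What 0.025 would change at 120 cases.** The smallest observed VE that rejects is 1 − 0.6 × exp(−2z/√120):

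- p = 0.0016: about 65%
- p = 0.00625: about 62%
- p = 0.025: about 58%

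**Type I error under selective use.** Suppose success is claimed at the look if p < 0.025, and otherwise the trial continues to 238 with final level c. With correlation √t between the two statistics,

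error = 0.025 + P(Z₁ ≤ 1.960, Z₂ > z_c).

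At 120 cases the second term is 1.47% (c = 0.02275) or 1.65% (c = 0.025).

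| Cases at look | t | c = 0.02275 | c = 0.025 |
|---|---|---|---|
| 120 | 0.504 | 3.97% | 4.15% |
| 150 | 0.630 | 3.76% | 3.92% |
| 180 | 0.756 | 3.50% | 3.65% |
| 220 | 0.924 | 3.01% | 3.14% |
| 237 | 0.996 | 2.56% | 2.65% |

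Binding futility lowers the 120-case row to 3.88% / 4.04%. Two looks (120 and about 178 cases) and a final, all at 0.025, give 4.85%.

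**Type I error under non-selective use.** If a first look is the only test whatever its result, the error is exactly 2.5%. If an unsuccessful interim at t = 0.5 is followed by one last test at 0.025 at t = 0.75, it is 2.5% (printed-formula boundary first) to 2.7% (0.00625 first).

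**The case against.** The clause is conditional. It does not say that any look between 120 and 237 cases may be tested at 0.025, only that full alpha applies when information is full. At a first look with t ≥ 1 that is correct. Swabs are tested in batches, so the count could pass 238 before any interim analysis is held. This reading is possible, but the 238-case rule already covers that situation, and the clause's reference to stopping enrolment fits an earlier look better.

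A reader might infer that full information can never be reached below 238 cases, so that the clause could only be an exception to the boundary. The documents do not support going that far. SAP 14.1 ties information to the accumulated variance of the estimate. If the maximum were set at the variance expected under HR 0.4 (an assumption; no maximum is stated), about 207 cases would reach it at HR 0.6 and about 219 at HR 0.5.

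A reader might also infer that the plan as written has a type I error of about 4%. That requires the DMC to invoke the clause because p < 0.025 and otherwise to continue, which the text does not direct. SAP 14.1 tells the DMC not to let interim efficacy results influence accrual or the timing of later analyses, and to plan from the overall case count alone. That is a partial guard, since it does not cover the full-information statement itself. The DMC charter, which is not available here, may say more.

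**Conclusion.** The concern stands as a conflicting decision rule that needs correcting, not as proof that the trial's error rate is 4%. Both documents allow a full-alpha test on an undefined declaration by an unblinded body, in a range of case counts where the spending plan allows less.

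The possible inflation runs from about 4.0–4.15% for a look at 120 cases down to about 2.6–2.65% at 237. It rests on selective use of the clause, one such look, a normal approximation with information proportional to cases, and no binding futility stop. The upper figure in each pair also contains the separate inconsistency between 0.025 and 0.02275 at the final analysis. Without selective use, a first look made the only test holds 2.5%.

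**What to change.** Delete the sentence in SAP 14.1 and Protocol 8.6, or replace it in both with:

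> Full information is 238 first-occurrence RT-PCR-confirmed cases in the primary window (or a prespecified maximum information level), determined without knowledge of the treatment effect. Any analysis before that uses the error-spending boundary for the observed information fraction. If the trial ends permanently before full information for reasons independent of the interim efficacy results, the last analysis uses the alpha not yet spent.

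The last sentence is needed because Protocol 3.6 lets the sponsor halt the study at any time; a trial that truly ends short of 238 cases should still be able to use its remaining alpha. If a maximum information level is chosen instead of the case count, its value must be written down.

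With this change every look before full information keeps its own boundary, and the overall error returns to 2.5%, provided the final-level inconsistency is resolved as well. The cost is wording in two documents, with the DMC charter checked for consistency. Sample size and conduct do not change. The sponsor gives up an informal route to an early test at full alpha.

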where HR is defined as hazard ratio of the incidence of protocol defined ILI in aQIV versus a non-influenza comparator that will be estimated by the proportional hazards model. More details on the analysis methods will be described in the Statistical Analysis Plan (SAP).		
The study is successful if the lower-limit (LL) of the two-sided 95% confidence interval (CI) (to be adjusted for one interim analysis) of absolute vaccine efficacy endpoint > 0.4 . In case another interim analysis is necessary the type 1 error alpha and hence the CI will be adjusted.		
Overall Study Success Criteria:		
The study is successful if the primary efficacy objective is achieved.		
Sample Size and Power Calculation for Primary Objective:		
Sample size and power consideration for the aQIV efficacy objective is based on criteria for demonstrating efficacy in placebo controlled studies provided in CBER guidance, specifically that the study should be powered to assess the lower bound of the two-sided 95% CI of vaccine effectiveness, anticipated to be substantially above zero.		
This study is planned using a group sequential design. The power of Cox Regression which is planned to be used for analysis is dependent on the overall number of RT-PCR		

Name of Sponsor: Seqirus UK Ltd.	Protocol number: V118_18	Generic name of study vaccine(s): MF59-adjuvanted Quadrivalent Subunit Inactivated Egg-derived Influenza Vaccine Tetanus Toxoid, Reduced Diphtheria Toxoid and Acellular Pertussis Vaccine, Adsorbed
confirmed influenza cases, so the sample sizes on number of subjects described in the sections above is provided more for operational reasons. Additional information is described in Section 8.6, Interim Analysis .		
For the primary efficacy objective: with 1-sided alpha of 2.5% (adjusted for possible interim analysis) and assuming an attack rate of influenza of 3.5% among subjects enroled in the non-influenza comparator group and 1.4% among the aQIV group, i.e. 60% assumed vaccine efficacy for aQIV, 238 events (i.e. 5,346 subjects per group under the assumed event rates (ER)) are needed with 86.5% power to show the absolute efficacy of aQIV versus non-influenza comparator, in preventing first occurrence RT-PCR confirmed influenza A and/or B, due to any strain of influenza regardless of antigenic match to the strains in aQIV, in subjects \geq 65 years of age, using a margin of 40% for lower bound of the CI for absolute vaccine efficacy ² .		

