3.6 Stopping/Pausing Guidelines

NP swabs will be analyzed in batches on a rolling basis throughout the study. When the number of RT-PCR confirmed influenza cases is between 119 and 238 interim analyses for efficacy and futility will be performed by an independent DMC. At least one interim analysis will be performed based on the number of RT-PCR confirmed influenza cases accrued at the time of the first interim analysis. After periodic review of safety and efficacy data, the DMC will make a recommendation as to whether enrolment in the study should continue, be stopped or paused (see [Section 8.6 Interim Analysis](#)).

Independent of the DMC, the Sponsor can halt the study at any time. If the study is halted, the Sponsor will promptly notify the health authorities and investigators, who will promptly inform the study subjects and local Ethics Committee/ Institutional Review Board (EC/IRB) as per local regulations. Study vaccinations and further enrolment will only occur after written authorization is provided by the Sponsor in conjunction with a recommendation to proceed by the DMC and in consultation with the health authorities and EC/IRB, as appropriate.

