12. EFFICACY ANALYSIS

12.1 Primary Objectives Analysis

The primary absolute efficacy objective will be evaluated using following null (H_0) and alternative (H_1) hypotheses:

$$H_0: 1 - HR = VE \leq 0.4 \quad \text{versus} \quad H_1: 1 - HR = VE > 0.4,$$

where HR is a hazard ratio of aQIV versus non-influenza comparator and VE is vaccine efficacy. The primary objective will be demonstrated if the lower limit of the two-sided confidence interval of VE estimate, with at least 95% coverage in a multiple sequential hypothesis testing, exceeds 40%. In case an interim analysis is performed, the 95% CI will be adjusted accordingly. If an interim analysis is performed and the trial doesn't stop, then all the subsequent analysis will be tested at a reduced alpha level, i.e. what's left from the interim analysis. The confidence interval will be higher than 95% instead of 95% for the final analysis.

Primary vaccine efficacy analyses will be based on the Efficacy FAS, and repeated on the Efficacy PPS.

The HR and the related 95% CI of HR, for onset of first RT-PCR confirmed influenza will be estimated by a proportional hazards regression model with treatment effect as a fixed effect and stratifying covariates as a random effect:

$h_i(t|X) = h_0(t) \exp(\beta^T X + b^T Z)$, with t denoting time to the influenza, β is the effect of treatment group indicated by X , b is random effect (assumed as a multivariable random gaussian variable with zero mean and diagonal covariance matrix), Z is random effect covariate (reflecting randomization strata, see [Section 8.1](#) for further discussion of the covariates utilised).

Subjects that did not experience ILI during observation period and subjects that dropped out from the study during observational period will be censored (right-censoring). The estimate of the hazard ratio, the respective estimate for absolute VE and the pertaining 2-sided CIs will be calculated based on this model. If the study continues over several seasons, estimates will be also adjusted for the factor season (s). In case of one or two (interim) analyses, confidence levels at each stage will be adjusted, as discussed in [section 14.1](#), to provide 95% overall coverage.

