12.2 Secondary Objectives Analysis

Hypotheses for testing secondary objectives are formulated in the similar way as for the primary efficacy objective. If an interim analysis is performed and the trial doesn't stop, then all the subsequent secondary analysis will be tested at a reduced alpha level, i.e. what's left from the interim analysis. The confidence interval will be higher than 95% instead of 95% at the final analysis.

All secondary efficacy objectives will be evaluated based on the Efficacy FAS, but analysis for the key secondary objective will be also repeated based on Efficacy PPS. For non-key secondary objectives, if the percentage of vaccinated subject excluded from the FAS is greater than 5%, a secondary analysis based on the PPS will be performed to complement the FAS.

Similarly to the primary efficacy objectives, a Cox PH model will be used to estimate absolute vaccine efficacy VE for each secondary objective 1-4.

Criteria for evaluation : if the lower limit of the 95% two-sided confidence interval for VE estimate is greater than 40% then the secondary efficacy objectives will be demonstrated.

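### After an interim efficacy look, the plan sets the final test both at the full one-sided 0.025 and at a reduced level

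*SAP*

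**What the plan says.** **Full level.** SAP 14.1 and Protocol 8.6 carry the same sentence for a trial that reaches the final analysis: "the boundary for rejection of null hypothesis is identical to the type 1 error (that is as the 0.025 one-sided alpha level". Both sections also allow a full-level final analysis on reaching 238 cases, or when the DMC judges that full information is available. Those statements can be read as covering only a trial with no earlier look.

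**Reduced level.** SAP 12.1 says that if an interim is done and the trial continues, "then all the subsequent analysis will be tested at a reduced alpha level", and adds: "The confidence interval will be higher than 95% instead of 95% for the final analysis". SAP 12.2 repeats this for the secondary objectives: "then all the subsequent secondary analysis will be tested at a reduced alpha level". The Protocol synopsis describes the success interval as "to be adjusted for one interim analysis". SAP 14.1 also says that at later stages "the boundary values are derived by using the test information tables created by the SEQTEST procedure at the previous stage". Table 1 in the SAP and Table 8.6-1 in the Protocol give a final boundary of 0.02275 after an interim boundary of 0.00625.

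**A third version.** Protocol 8.2.1.2, 8.2.2.2 and 8.4.2.2.3 mention adjusting the confidence level when there is more than one interim. Protocol 3.6 says: "At least one interim analysis will be performed".

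**Within SAP 12.2.** After asking for an interval above 95%, the section declares the objectives demonstrated "if the lower limit of the 95% two-sided confidence interval for VE estimate is greater than 40" per cent.

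**The concern.** The primary objective succeeds or fails on whether the lower limit for vaccine efficacy exceeds 40%, and the confidence level of that limit has to be fixed before unblinding. A reader who follows the 0.025 sentence uses Z = 1.960. A reader who follows SAP 12.1 uses whatever the spending function leaves. SAP 12.1 refers to section 14.1 for the adjustment, and section 14.1 then states 0.025, so the cross-reference does not settle the matter.

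The sequential software would settle it only if its inputs agreed, and they do not:

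- **Spending function:** SAP 14.1 names an O'Brien-Fleming type function; SAP 14.1.1 refers to a power function.
- **Type 2 error:** SAP 14.1 and 14.1.1 use 0.1; SAP section 5 states 86.5% power, a type 2 error of 0.135.
- **Futility:** SAP 14.1 and Protocol 8.6 say the trial stops when the futility boundary is crossed, but Protocol 8.6 also leaves the decision to discussion between the DMC and the sponsor's management. Neither document says whether the boundary is binding.

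**Working it through.** **Inputs.** Overall one-sided alpha 0.025, null HR 0.6, assumed HR 0.4, 1:1 allocation, 238 events, 86.5% power (SAP 5 and 12.1). Spending function, beta 0.1 and example boundaries 0.00625 / 0.35022 / 0.02275 at 119 and 238 events (SAP 14.1). Information fraction t = look/238; correlation of the two test statistics √t. Drift at 238 events = ln(0.6/0.4) × √(238/4) = 3.128.

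**1. Reproducing the example table.** A power-family function with exponent 2 spends 0.025 × 0.5² = 0.00625 at half information. With beta 0.135 and binding futility, the two-stage calculation gives 0.00625, 0.35022 and 0.02275, and needs 238.3 events. At drift 3.128 these boundaries have 86.45% power (86.5% stated). The table is internally sound.

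**2. The function named in the text.** At half information the O'Brien-Fleming type function spends 2 × [1 − Φ(2.2414/√0.5)] = 2 × [1 − Φ(3.170)] = 0.00153, not 0.00625. For a look at 119 the final level is then:

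- 0.0245 with non-binding futility (interval 1 − 2 × 0.0245 = 95.1%);
- 0.0253 with binding futility and beta 0.1, or 0.0256 with beta 0.135.

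At this look, SAP 12.1's interval above 95% therefore holds only if futility is non-binding.

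**3. Overall one-sided error when the final test is at 0.025.** Error = P(Z1 > c1) + P(continue at stage 1, Z2 > 1.960) under the null.

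- Example table's interim boundary at 119 (c1 = 2.498): 2.80% non-binding, 2.69% binding.
- O'Brien-Fleming type, non-binding:

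| Look (cases) | Error at 0.025 | Final p that keeps 2.5% | Z |
|---|---|---|---|
| 119 | 2.55% | 0.0245 | 1.969 |
| 143 | 2.62% | 0.0238 | 1.981 |
| 167 | 2.71% | 0.0227 | 2.000 |
| 200 | 2.84% | 0.0209 | 2.036 |
| 215 (peak) | 2.86% | 0.0200 | 2.054 |

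- Two O'Brien-Fleming type looks at 119 and 179, non-binding: 2.77%.
- O'Brien-Fleming type, strictly binding, beta 0.135: 2.44% to 2.48% with the drift solved for the design, and at most 2.50% with the drift fixed at 3.128.
- O'Brien-Fleming type, strictly binding, beta 0.1: at most 2.51% with the drift solved, but up to 2.72% (look at 224) with the drift fixed at 3.128.

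**4. Effect on the decision.** With x aQIV cases out of D, and equal follow-up assumed, success requires ln(x/(D − x)) + Z × √(1/x + 1/(D − x)) < ln 0.6.

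- **Final, D = 238:** at x = 74 the left side reaches ln 0.6 when Z = (−0.5108 + 0.7958)/0.1400 = 2.035. The cut-off is therefore 74 for Z = 1.960, 1.969, 2.000 and 2.018, and 73 for Z = 2.036.
- **Interim, D = 119:** the cut-off is 31 aQIV cases at 0.00625 and 28 at 0.00153. With 29 to 31 cases the table says stop and the named function says continue.

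**The case against.** The intended rule is stated many times. Protocol 8.6 uses error spending to hold the overall one-sided 2.5%, Protocol 8.4.2.2.3 takes the final interval from the group-sequential method, and SAP 8.4 adjusts for each stage. On this view the 0.025 sentences are stray wording. Full 0.025 is also correct if 238 cases arrive with no earlier look, which the plan allows. The table is headed as an example, with actual boundaries depending on the case count. Protocol 8.6 and SAP 14.1 rule out an interim at 119 cases or fewer, so the 119 figures are illustrative. The wording about more than one interim may mean a further adjustment, since the synopsis already adjusts for one. Whether futility is binding may be settled in the DMC charter, which is not available here.

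Most of this is fair as to weight. The intended rule is recoverable, and the impact is small. At 120 cases the named function gives 0.00160 and 0.0245, almost the same as at 119. None of it removes the conflict. The 0.025 sentence is not limited to the no-look path, and further passages requiring adjustment only sharpen the contradiction. The example label does not explain boundaries that differ from the named function at exactly the information fraction shown. A charter cannot correct a sentence in the SAP.

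**Conclusion.** The concern holds and should be fixed. As written, the plan gives two levels for the final primary test after an efficacy look, and its example boundaries do not come from the method it names. This is conflicting wording and not a missing method: SAP 12.1 and the sequential-testing paragraph of SAP 14.1 already contain the right rule.

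The size is modest. The overall one-sided error is at most 2.80% with one look at the example table's interim boundary, and 2.55% to 2.86% with one non-binding O'Brien-Fleming type look between 119 and 215 cases. Under strictly binding O'Brien-Fleming type futility there is little or no excess, apart from beta 0.1 with the drift fixed at 238 events. The final cut-off moves by at most one case over the Z values checked (1.960 to 2.036). These figures rest on the normal approximation with event-based information; the cut-offs also assume equal follow-up in the two groups.

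**What to change.** 1. In SAP 14.1 and Protocol 8.6, limit the 0.025 and full-alpha sentences to a trial in which no unblinded efficacy look has occurred. Otherwise the final level and interval are those the spending function leaves after the looks actually taken.
2. In Protocol 8.2.1.2, 8.2.2.2 and 8.4.2.2.3, make the adjustment apply to one or more interims. In the SAP 12.2 criterion, replace 95% with the adjusted level.
3. State one spending function, one beta and whether futility is binding. Recalculate Table 1 and Table 8.6-1 to match, and correct the word power in SAP 14.1.1 if the O'Brien-Fleming type function is kept. As an illustration, one such look at 119 cases with non-binding futility gives 0.00153 and 0.0245.
4. As a minor point of notation, define Z in SAP 12.1 as the 100(1 − α/2) percent point.

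The cost is wording, one design choice and one recalculated table. With O'Brien-Fleming type spending and non-binding futility, the power of the final test alone at 238 events, Φ(3.128 − Z), goes from 87.9% at Z = 1.960 to 87.7% (look at 119) or 86.2% (look at 200). Counting the chance of rejecting at the interim, power with a look at 200 is 87.2%.
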